4.2.2 Recruitment

The primary recruitment for this study will be through participating NF Consortium Centers and orthopaedic centers. This prospective clinic trial will be posted on websites and included in the newsletters of the NF support organizations (CTF and NF Network). Directors and coordinators at each of the 42 clinics affiliated with the CTF NF Clinic Network will be notified of the trial and eligibility.

A total of between 36-52 patients will be enrolled prospectively in this trial. The maximum number of patients that will be enrolled in the BMP arm is 26, based on the numbers of Infuse kits supplied by the sponsor. The ideal number of Control patients is also 26, but may range from 10-26, based on preferences of enrollees. This is further discussed in the Study Modification section below, 4.2.3. We expect that dropout rate of participants, once they have been enrolled and had their surgical procedure performed, should be very low, in the range of 5%. The experience of participating surgeons is that their TPA patients who have had surgery are extremely likely to attend subsequent follow-up visits. The final endpoint of the trial is at the one-year assessment of the last patient enrolled. Due to slow enrollment in the first year of the trial, we have added 5 Shriners orthopedic centers in the U.S. as participants in the trial. Funding has been included to help support family travel as outlined, in the Informed Consent forms (range of \$200-\$500 per patient, with the greater amount for patients living further than 50 miles from the participating center). Participants who live further than 50 miles from a participating center may have an option to elect to have several of the follow-up visits and Xrays (3 and 9 months post-op) performed by their local orthopedic surgeon, with results sent to the DMAC and radiographic team at TSRH. However, the surgical procedure and follow-up visits at 6 and 12 months must be at a participating center with either the orthopaedic surgeon or the NF specialist. All centers performing any subject evaluations for the study must have completed the appropriate mandatory electronic training modules prior to performing any assessments.

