We anticipate that this would leave the study with a potential slight imbalance in BMP treatment and controls. Thus, we evaluated the impact on the primary analysis given various scenarios on recruitment and testing treatment effects assuming the results of choice and randomized allocation could be pooled.

The study is limited by the company's allocation of just 26 BMP devices, so we examined the power of the study under various scenarios of BMP treated to Controls. The table below shows the power, along with the sample sizes (shown in italics in the table in the 4th and 5th rows), if the study ends up with 5 and 26 patients in Usual Care versus BMP, up to comparison of 20 Usual Care versus 26 BMP across the columns of the table. The power ranges from 46% power to detect a difference in RUST scores using a 1 tailed test at 0.05 to over 80% (as per our original primary analysis and endpoint). This is testing the RUST scores assuming UC of: 33% (Rust Scores 4-7), 42% (8-9) and 25% (10-12) compared to 15% (4-7); 20% (8-9) and 65% (10-12). So if we enroll at least 10 -15 controls, we have approaching 70% power to declare a significant difference. Obviously, we need to have a sufficient number of controls to enhance the power, and to help ensure this result, we will randomize 3 controls to 2 BMP cases in the randomization to enhance our ability to achieve at least 10 controls.

**Power using a Wilcoxon (Mann-Whitney) rank-sum test that $P(X < Y) = .5$ (ordered categories) (unequal n's), One sided Type I error=0.05
(Control Rust scores 33% (4-7), 42% (8-9), 25% (>=10) versus BMP 15%, 20%, 65% respectively)**

	1	2	3	4	5	6	7	8
Number of categories, k	3	3	3	3	3	3	3	3
$p_1 = P(X < Y)$	0.702	0.702	0.702	0.702	0.702	0.702	0.702	0.702
Power (%)	46	51	56	59	62	65	76	82

n_1	26	26	26	26	26	26	26	26
n_2	5	6	7	8	9	10	15	20

Our analysis will be a primary analysis combining the Choice and randomized participants. We will perform sensitivity analyses within the Choice and Randomized cohorts separately. Given the limited sample sizes, we do not expect significant differences, but will examine descriptive statistics comparing the Choice Group to the Randomized Group. We will examine the RUST scores amongst those who choose BMP versus those who refuse and choose usual care. We will of course, consider comparisons to historical controls should the results prove clearly different between the Choice and Randomized Groups.

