While BMP-2 has been evaluated extensively in non-NF1 patients, it has not been administered as a clinical trial in children with NF1 who have tibial pseudarthrosis. An early stopping rule will be invoked to prevent accrual of patients onto the study in the event that BMP-2 is associated with a higher than acceptable rate of severe toxicity identified at 6 weeks and 12 weeks post surgery [types: Grade 3 opportunistic infection, Grade 4 rash, Grade 3 hypertension, grade \geq 3 allergic reaction (determined by clinical assessment and antibody levels), grade 3 renal toxicity, severe ectopic bone formation requiring surgery, or the development of malignant peripheral nerve sheath tumor or other cancers]. Toxicity assessment will be graded according to the National Cancer Institute Common Terminology Criteria for Adverse Events (CTCAE) (v4.03). After 10 patients are enrolled in each arm, toxicity will be reviewed and if greater than the

number of patients shown in the table below experiences severe toxicity, accrual will be stopped. Based upon results calculated using the binomial distribution, the following holds true for the table as a whole:

True probability of toxicity	Chance of stopping early
.10	7%
.20	32%
.25	47%
.30	62%
.40	83%

Number of patients	Trial will be stopped if the number of patients with severe toxicity is greater than or equal to the number below
10	3

Should the number of patients showing severe toxicity during treatment with BMP-2 exceed 25% of the total number of patients enrolled, the study committee and medical monitor will review the toxicities and define whether a protocol revision is required. This 25% level was determined based on prior studies showing a total complication rate of 17% in pediatric patients treated with BMP-2 [[name] and [name], 2010].

Likewise, the trial may be stopped early if at least 6 patients of the first 10 enrollees in the BMP-2 arm have complete failure of union by 12 months postop (RUST score of 5 or less). This will be determined after the first 10 enrollees in the BMP-2 arm have completed the 12 month assessment. The entire study will be terminated if the BMP-2 group is stopped early due to toxicity or failure of union.

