Since subjects, once they have had surgery, will need to be seen regularly for follow-up, we expect little or no attrition or loss to follow-up. Therefore, we will plan to enroll a total of between 36-52 patients, with a minimum goal of 15 eligible patients in the control arm and 26 patients in the BMP arm.

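### The BMP-2 toxicity stopping sentence contradicts its own table, its review is worded to wait for ten controls, and the 25% review prompt divides BMP-2 toxicities by all enrolled patients

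*Combined protocol and SAP*

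**What the plan says.** All three elements stand under Early Stopping Rule in section 6.2 of the combined protocol and SAP.

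- **Stopping sentence.** "After 10 patients are enrolled in each arm, toxicity will be reviewed and if greater than the" number of patients in the table that follows, accrual stops. The toxicities concerned are those identified at 6 and 12 weeks after surgery.
- **Table.** For 10 patients the tabled number is 3, under the heading "Trial will be stopped if the number of patients with severe toxicity is greater than or equal to the number below". A companion table, said to be binomial, prints the chance of stopping as 7, 32, 47, 62 and 83% at true toxicity rates of .10, .20, .25, .30 and .40.
- **25% level.** "Should the number of patients showing severe toxicity during treatment with BMP-2 exceed 25% of the total number of patients enrolled", then "the study committee and medical monitor will review the toxicities and define whether a protocol revision is required". The stated basis is a 17% total complication rate in children treated with BMP-2.
- **Failure-of-union rule, same subsection.** It counts BMP-2 patients only: "This will be determined after the first 10 enrollees in the BMP-2 arm have completed the 12 month assessment".

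On numbers, section 4.2.2 caps the BMP arm at 26 and says of controls: "The ideal number of Control patients is also 26, but may range from 10-26, based on preferences of enrollees". Section 6.2 closes "with a minimum goal of 15 eligible patients in the control arm and 26 patients in the BMP arm". It also expects families to prefer BMP-2, which is why "we will randomize 3 controls to 2 BMP cases in the randomization to enhance our ability to achieve at least 10 controls".

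**The concern.** This is the pre-specified rule that limits further exposure of children to BMP-2, and section 5.7 relies on it as a protection. Three things in it do not fit its purpose.

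1. The sentence and the table give opposite instructions at exactly 3 severe toxicities in 10. A team that follows the sentence uses a laxer rule than the one whose operating characteristics are printed.
2. Controls contribute nothing to a count of BMP-2 toxicities, yet the look is worded to wait for ten of them, in a design where controls are expected to be the scarcer group. The trigger also counts enrolments, although toxicity is known only 6 to 12 weeks after surgery.
3. The 25% level has a BMP-2 numerator and an all-patient denominator, while its benchmark is a rate among BMP-2-treated children. Every control enrolled makes the prompt harder to reach.

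**Working it through.** **1. Which boundary do the printed chances support?**

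Inputs: n = 10 and the five true rates, from the Early Stopping Rule tables. Formula: P(X ≥ r) = Σ C(10,k) p^k (1−p)^(10−k), summed over k = r to 10.

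| True rate | Printed | r = 3 (table) | r = 4 (sentence) |
|---|---|---|---|
| .10 | 7% | 7.0% | 1.3% |
| .20 | 32% | 32.2% | 12.1% |
| .25 | 47% | 47.4% | 22.4% |
| .30 | 62% | 61.7% | 35.0% |
| .40 | 83% | 83.3% | 61.8% |

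Three or more reproduces all five figures; more than three reproduces none.

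**2. How long might the look wait for controls?**

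Inputs: 26 BMP patients and 10 to 26 controls (section 4.2.2), with 15 controls as the minimum goal (end of section 6.2). Assumption: enrolment order is random with respect to arm. With m controls in total, the expected number of BMP patients enrolled before the tenth control is 26 × 10/(m + 1).

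- m = 10: 260/11 = 23.6
- m = 15: 260/16 = 16.3
- m = 20: 260/21 = 12.4
- m = 26: 260/27 = 9.6

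With even accrual the delay vanishes. With 10 controls nearly all BMP-2 exposure precedes the look. With fewer than 10 the condition is never met.

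**3. What does the 25% level require?**

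The smallest count exceeding 25% of N is floor(0.25 N) + 1. The chance of reaching it at a single look with all 26 BMP patients enrolled is binomial with n = 26.

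| Denominator | N | Count needed | As share of 26 BMP | Chance at true 40% |
|---|---|---|---|---|
| All enrolled, 10 controls | 36 | 10 | 38% | 64% |
| All enrolled, 15 controls | 41 | 11 | 42% | 48% |
| All enrolled, 26 controls | 52 | 14 | 54% | 11% |
| BMP-2 patients only | 26 | 7 | 27% | 94% |

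The plan does not say when the level is checked, so a single late look is only one end of the range. At the other end, it is checked after every enrolment. This was simulated with 100,000 runs, random order and a true rate of 40%. Starting at the tenth enrolled patient, the chances are about 89, 80 and 58% with 10, 15 and 26 controls. On a BMP-2 base, starting at the tenth BMP patient, the chance is about 98%.

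**4. How much of the loss does the three-of-ten stop recover?**

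The same simulation was run for the chance that either safeguard fires: three or more among the first ten BMP patients, or the continuously checked 25% level.

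| True rate | All enrolled: 10 / 15 / 26 controls | BMP-2 base |
|---|---|---|
| 40% | 91 / 88 / 84% | 98% |
| 30% | 69 / 65 / 62% | 85% |

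**The case against.** The strongest reply has five parts.

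- **The boundary slip resolves itself.** The table and every printed chance agree, and the sentence refers to the table. It is true that the intended rule can be recovered. The protocol still gives two answers at 3 of 10, the one result where the rule's wording decides the outcome.
- **The phrase about each arm may be distributive**, so that each arm is reviewed at its own tenth patient. The table's single row of 10 patients fits that reading, as does the later statement that the study ends if the BMP-2 group is stopped. The reading is possible but not the plain one, and the adjacent failure-of-union rule shows how to name BMP-2 patients alone. Fewer than 10 controls also lies outside the enrolment range, although the power table goes down to 5.
- **Random order may overstate the delay.** The trial began as a randomised design planned at 25 per group, and choice was added after the first year, so early accrual may have been more balanced. First-year counts by arm are not given, so the size of this effect is unknown.
- **The 25% level is secondary.** It leads to a review and not a stop, and the three-of-ten rule would catch much of a high rate first. That stands. With both safeguards counted and continuous checking, the loss at a true 40% rate is 7 to 14 points and at 30% about 16 to 23 points, well short of the single-look contrast.
- **Other protections exist.** Expedited reporting is mandatory and covers serious events within 30 days of device placement (section 5.9). A DSMB monitors adverse events regularly, and the research monitor must review serious events and may halt the trial (section 6.4). These limit the harm, but any decision to stop through them is discretionary and does not mend the formal rule.

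**Conclusion.** The concern holds in all three parts and should be fixed.

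- **Boundary.** Certain from the text and exact arithmetic. The table is right and the sentence wrong. Following the sentence would cut the chance of stopping at a true 30% rate from 62% to 35%.
- **Timing.** Follows from the plain reading. Its size depends on the final number of controls and on random enrolment order: negligible with even accrual, and a look after about 16 of 26 BMP patients with 15 controls or about 24 with 10.
- **Denominator.** The mismatch is certain. Its effect depends on the unstated checking schedule and on whether the three-of-ten stop is counted alongside it, as quantified above.

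**What to change.** 1. In the sentence, replace the strict inequality with three or more, to match the table. The table and the printed chances stay as they are.
2. Key the toxicity review to the first 10 BMP-2-treated patients with 12-week toxicity assessments, and stop accrual as soon as a third severe toxicity occurs among them. Reaching three within the first ten is the same event whether it is noticed at once or at the end, so the printed chances still apply. Stopping at the third event goes a little beyond correcting the text. It is there because waiting for 12-week data could make the formal review slightly later if the arms accrue evenly.
3. Use BMP-2-treated patients as the denominator of the 25% level, and state when it is checked.

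The clinical thresholds (3 of 10 and 25%) remain for the sponsor and the DSMB to set.

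The cost is wording in the protocol and in any DSMB charter, with no added patients or data. A BMP-2 denominator will also prompt more reviews when toxicity is acceptable. At a true 17% rate, a single look at 26 BMP patients prompts a review 14% of the time (7 or more), against 0.8% on the all-enrolled base with 10 controls (10 or more). The consequence is a committee review, so this is a small price.

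### The 25% toxicity trigger is a share of all enrolled patients, controls included, so it needs severe toxicity in 38–54% of 26 BMP-2 patients, although its stated basis is a rate among BMP-2-treated children

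*Combined protocol and SAP*

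**What the plan says.** The Early Stopping Rule in section 6.2 has two toxicity provisions.

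- **A look at 10 patients per arm.** Accrual stops if at least 3 patients have one of the listed severe toxicities. A table gives the chance of stopping at five true rates.
- **A running trigger.** It reads "Should the number of patients showing severe toxicity during treatment with BMP-2 exceed 25% of the total number of patients enrolled", and then "the study committee and medical monitor will review the toxicities and define whether a protocol revision is required". The reason for the level follows: "This 25% level was determined based on prior studies showing a total complication rate of 17% in pediatric patients treated with BMP-2". No operating characteristics are given for this trigger.

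Elsewhere the enrolment total means both groups together. Section 4.2.2 has "A total of between 36-52 patients will be enrolled prospectively in this trial", with "The maximum number of patients that will be enrolled in the BMP arm is 26" and "The ideal number of Control patients is also 26, but may range from 10-26". Section 6.2 closes with the same range, "we will plan to enroll a total of between 36-52 patients", and gives the intended split by arm: "with a minimum goal of 15 eligible patients in the control arm and 26 patients in the BMP arm".

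**The concern.** The numerator can come only from patients who received the device, at most 26. The denominator, on its natural reading, also includes 10 to 26 controls who never receive it. The 25% level is defended by a rate per treated child. The threshold and its stated basis therefore use different denominators.

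Two things follow. The trigger corresponds to a BMP-2 toxicity rate well above 25%. That rate also rises as controls enrol, although controls carry no information about device toxicity. Toxicity of BMP-2 in this population is Objective 2, and section 6.2 notes that the product has not been tested in a clinical trial in these children. At stake is whether the one numerical trigger that operates after the 10-patient look would respond to a rate that the plan itself treats as calling for review.

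**Working it through.** **1. The plan's own table.** The chance of at least 3 events in 10 patients, X ~ Binomial(10, p), is 7.0%, 32.2%, 47.4%, 61.7% and 83.3% at p = 0.10, 0.20, 0.25, 0.30 and 0.40. The plan prints 7%, 32%, 47%, 62% and 83%, so all five are reproduced. More than 3 of 10 gives 1.3% to 61.8%, and at least 3 of 20 gives 32.3% to 99.6%; neither fits. The table is therefore a count in a single group of 10 with a boundary of 3 or more. I take that group to be the first 10 BMP-2 patients.

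**2. Events needed for the 25% trigger.** To exceed 25% of N takes r = floor(0.25 × N) + 1 events. The implied BMP-2 rate is r divided by the number of BMP-2 patients.

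| BMP-2 v control | N | 25% of N | Events needed | Share of BMP-2 patients |
|---|---|---|---|---|
| 26 v 10 | 36 | 9 | 10 | 38% |
| 26 v 15 | 41 | 10.25 | 11 | 42% |
| 26 v 20 | 46 | 11.5 | 12 | 46% |
| 26 v 26 | 52 | 13 | 14 | 54% |
| 26, BMP-2 denominator | 26 | 6.5 | 7 | 27% |
| 10 v 10 | 20 | 5 | 6 | 60% |
| 10, BMP-2 denominator | 10 | 2.5 | 3 | 30% |

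At 10 v 10 the review trigger needs 6 events, twice the 3 that already stop accrual. With a BMP-2 denominator it needs 3 of 10, the same count as the tabulated boundary.

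**3. What the trigger adds after a passed look.** The documents give no expected severe-toxicity rate for this population, so 30% and 40% are illustrative assumptions. I assume one check, with all 26 BMP-2 patients enrolled. A trial passes the look with k = 0, 1 or 2 events in the first 10, and the trigger then needs r − k of the remaining 16:

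P(pass and trigger) = Σ over k = 0, 1, 2 of P(X₁₀ = k) × P(X₁₆ ≥ r − k).

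Example at 30%, r = 7 (BMP-2 denominator):

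- P(pass) = 0.0282 + 0.1211 + 0.2335 = 0.3828.
- P(pass and trigger) = 0.0282 × 0.1753 + 0.1211 × 0.3402 + 0.2335 × 0.5501 = 0.1746.
- Given a pass: 0.1746 / 0.3828 = 46%.
- Either rule fires: 0.6172 + 0.1746 = 79%.

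| | BMP-2 denominator (r = 7) | 10 controls (r = 10) | 15 controls (r = 11) | 26 controls (r = 14) |
|---|---|---|---|---|
| 30%: trigger met, given a pass | 46% | 5% | 2% | 0.02% |
| 30%: either rule fires | 79% | 64% | 62% | 62% |
| 40%: trigger met, given a pass | 78% | 24% | 12% | 0.4% |
| 40%: either rule fires | 96% | 87% | 85% | 83% |

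With 26 controls, a trial that has passed needs at least 14 − 2 = 12 events in its last 16 BMP-2 patients. The look alone fires with probability 62% at 30% and 83% at 40%, so with equal groups the trigger adds almost nothing.

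**The case against.** **The authors probably meant BMP-2 patients only.** The numerator, the 17% rationale and the agreement with 3 of 10 all point that way. This is likely, and no printed figure is miscalculated. But the text does not say it, and a committee applying the words literally would wait for 10 to 14 events.

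**Other oversight exists.** A reader might infer that no review starts until more than half of the BMP-2 children have severe toxicity, or that Objective 2 is left unprotected. The documents do not support either. More than half is a feature of equal groups; section 6.2 expects fewer controls, and with 10 to 20 of them the figure is 38–46%. The 10-patient stop is unaffected. Section 6.4 provides a safety board that monitors adverse events and a research monitor who reviews serious events and can stop the protocol. Section 5.9 requires expedited reporting. None of these carries a numerical toxicity threshold after the 10-patient look, so they limit the consequence without repairing the rule.

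**The effect looks larger if the earlier look is ignored.** Taken alone at 30%, the trigger is met with probability 70% on a BMP-2 denominator and 1% at 26 v 26. That contrast overstates the practical loss, because the 3-of-10 stop comes first; the either-rule figures are the fair measure. Repeated checks during accrual would raise the values, and the plan fixes no time for the check.

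**The 17% is not a severe-toxicity rate.** Sections 2.2.2 and 3.5.2 give it as a total complication rate, mostly wound inflammatory responses, whereas the trigger counts only listed severe events. This stands. Reading the effective threshold as two to three times an expected severe rate would compare unlike quantities.

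**Conclusion.** The point holds: a stated decision threshold does not match its stated basis. As written, the trigger needs 38–54% of 26 BMP-2 patients to have severe toxicity, depending on how many controls enrol, instead of 27%. These counts rest only on the wording and on the plan's group sizes.

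In the period it is meant to cover, after a passed 10-patient look, the trigger is close to inert: 0.02–5% against 46% at a true rate of 30%, and 0.4–24% against 78% at 40%. The loss in the chance that at least one rule fires is smaller: 79% to 62–64% at 30%, and 96% to 83–87% at 40%. These probabilities assume the illustrative rates, independent events, the first 10 BMP-2 patients at the look, and one check at full enrolment. They do not show that toxicity would go unnoticed, because the non-numerical oversight continues, and the trigger leads to a review rather than a stop.

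**What to change.** In the Early Stopping Rule of section 6.2, reconcile the denominator with its stated basis: express the 25% as a share of the patients treated with BMP-2 to date. The trigger is then 7 of 26 whatever the number of controls, and 3 of 10 at the first look.

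In the same paragraph, state that the 17% is a total complication rate while the trigger counts only the listed severe toxicities, so that changing the denominator is not taken to make the two figures equivalent.

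The cost is a few words in an amendment and somewhat more frequent reviews by the study committee and medical monitor. Sample size, endpoint, primary analysis and the 10-patient stop do not change.

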 - Cast time may be extended in 4-6 week intervals, followed by radiographic re-evaluation until satisfactory healing has been achieved.
 - If casting is required beyond 3 months, it may be below-the-knee instead of above-the-knee.
- Braced (above or below knee) with partial weight-bearing beginning at 3 months
- Knee mobilization exercises beginning at 3 months (or after removal of cast if later than 3 months).
- Full weight-bearing (braced) based on X-ray appearance (RUST score of 9 or greater)
- No sports participation until 1 year post-operative and with brace in situ.
- Individual questions about rehabilitation protocol may be addressed to the two study surgeons (Drs. [name] and [name]).

5.3 Protocol to Radiographically Score Tibial Healing (RUST score, Primary Outcome Measure; Specific Aim 1)

The assessment of tibial healing in patients with tibial pseudarthrosis will be based on radiographic evidence of union by determination of cortical continuity on X-ray and scoring by a novel system called the Radiographic Union Score for Tibial fractures (RUST) score [Whelan et al., 2010]. This validated method assigns a score to a set of anteroposterior (AP) and lateral (Lat) radiographs based on healing at each of the 4 cortices. The lateral and medial cortices are denoted on the AP radiograph and the anterior and posterior cortices on the lateral radiograph. A score of 1-3 is assigned based on the persistence of the fracture line and the presence or absence of callus formation. If all 4 cortices are evaluable then scores range from 4 (non-union all bone columns) to 12 (complete union of all 4 bone columns). As this method was validated in fractured normal tibias, any lucency was considered residual fracture. However, in these patients there is known underlying dysplasia affecting the appearance of the bone underlying the osteotomy; therefore an intact peripheral cortex with residual intramedullary dysplasia will be considered healed. A cortex that is not visualized due to eccentric overlying hardware will be given a value of 1.

Scoring system:

1 = no new calcification, or rod eccentricity precludes evaluation

2 = new calcification or callus present

3 = smooth continuous outer cortex, even if underlying lucency

Total score ranges from 4 to 12.

For the purpose of this study, a RUST score of 9-12, with at least 2 evaluable cortices having a score of 3, will be considered to be healed, and a successful outcome.

Figure 6: RUST scoring

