6.2 Power Analysis/Sample Size Justification

The primary study endpoint will be the subject's RUST score 12 months after surgery. The radiology panel determining RUST score will be blinded to the treatment status of all patients, whether in the Choice or Randomized arms. The two treatment groups will be compared with

respect to the RUST score using the Wilcoxon Rank Sum Test at the one sided 0.05 significance level.

Data from the TSRH of 12 patients treated without BMP but an identical surgical protocol showed RUST scores at 12 mos post surgery of: Score 4-7 in 33%; Score of 8-9 in 42%; and score of 10-12 in 25%. If the use of BMP improves these scores to: 15% 4-7; 20% 8-9, and 65% 10-12, as suggested by our data from [name] 16 patients treated with BMP, then it follows that for two patients randomly chosen, one from each treatment group, the probability that the patient in the BMP group will have a better score than the patient in the Control group is .691. Using a standard formula [Kolassa, 1995] implemented in nQuery Advisor® 7.0 this study with the initially planned sample size of 50 (25 per group) will have 86% power for a Wilcoxon Rank Sum Test at the one sided p.05 significance level.

Study Modification: Based on data from the first year of the trial, more eligible patients declined to participate than agreed to participate; however, in many of these cases the family would have agreed to a Parental Preference trial. Similar Parental Preference clinical trials have achieved acceptance within the orthopedic field, as demonstrated by the large BrAIST study of bracing versus no bracing for adolescent scoliosis [Weinstein et al, 2013; Schwieger et al., 2016]. The study was thus modified after initiation to allow a **Choice Group**, wherein after offering whether a potential participant had a preference, this would be honored. If there were no preference or if there is no option to obtain BMP at the institution where the participant is being seen, they would be **randomized** to BMP or Control using a 2:3 randomization. The rationale for this unbalanced randomization is to obtain or achieve enough controls to have a reasonable comparison of the effect of BMP. It is expected by participating surgeons that more patients would prefer the BMP arm to the Control arm if given the choice.

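### The non-union stopping decision waits for all ten 12-month assessments even when six failures are already recorded; acting at the sixth costs nothing and brings the decision modestly forward

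*Combined protocol and SAP*

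**What the plan says.** The rule is in Section 6.2, Early Stopping Rule, after the toxicity boundary. The wording is permissive: stopping is allowed, not required, "if at least 6 patients of the first 10 enrollees in the BMP-2 arm have complete failure of union by 12 months postop". Such a failure is defined there as a RUST total no higher than 5. A separate sentence sets the timing: "This will be determined after the first 10 enrollees in the BMP-2 arm have completed the 12 month assessment". The section then says that the entire study ends if the BMP-2 group is stopped for toxicity or failure of union.

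For toxicity (3 or more of 10), the section prints the chance of stopping at five true rates. It prints none for the non-union rule. It makes no provision for acting before the tenth assessment and none for pausing BMP-2 enrolment meanwhile.

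The planning data for the control group are also in Section 6.2: "Data from the TSRH of 12 patients treated without BMP but an identical surgical protocol", of whom 33% scored 4-7, 42% scored 8-9 and 25% scored 10-12 at 12 months. The BMP-2 arm is capped at 26 patients (Sections 4.2.2 and 6.2).

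**The concern.** The boundary is a count, and a count of failures can only rise. Once six of the first ten BMP-2 children have a 12-month RUST score of 5 or less, the remaining assessments cannot take the arm back below the boundary. The timing sentence nevertheless puts the decision after the tenth child's visit. Any child given the implant in between is treated after the plan's own criterion has been met, and the wait gives no statistical protection in return. At stake are a few months and a small number of implants, in the one scenario the rule exists to catch.

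**Working it through.** **Check of method against the plan's own figures.** Toxicity rule, exact binomial P(X ≥ 3 | n = 10, p):

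| True rate | Printed | Recomputed |
|---|---|---|
| 0.10 | 7% | 7.0% |
| 0.20 | 32% | 32.2% |
| 0.25 | 47% | 47.4% |
| 0.30 | 62% | 61.7% |
| 0.40 | 83% | 83.3% |

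All five reproduce, so the same binomial is used below.

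**Step 1: acting at the sixth failure does not change the stopping chance.** The event that at least 6 of the first 10 fail is identical to the event that the sixth failure occurs at or before enrollee 10. Only the date differs.

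**Step 2: where the sixth failure falls.** If each child fails with probability p, the sixth failure falls on enrollee n with probability C(n−1, 5) p^6 (1−p)^(n−6). The documents give no failure rate for this scenario, so p = 0.60 is assumed:

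- n = 6: 0.0467
- n = 7: 0.1120
- n = 8: 0.1568
- n = 9: 0.1672
- n = 10: 0.1505

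The sum is 0.633, the chance of reaching the boundary. Before the tenth: 0.4826 / 0.6331 = 76%. Mean position, given that the boundary is reached: 5.328 / 0.6331 = 8.4, so the decision moves forward by 10 − 8.4 = 1.6 enrollees.

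The same formula at neighbouring assumed rates:

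| p | Boundary reached | Before the tenth, if reached | Mean enrollee, if reached | Gain (enrollees) |
|---|---|---|---|---|
| 0.50 | 37.7% | 0.2539/0.3770 = 67% | 3.293/0.3770 = 8.7 | 1.3 |
| 0.60 | 63.3% | 76% | 8.4 | 1.6 |
| 0.70 | 85.0% | 0.7297/0.8497 = 86% | 6.769/0.8497 = 8.0 | 2.0 |

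**Step 3: what that is in time and implants.** Accrual is assumed even: 26 BMP-2 patients over A years, with visits at exactly 12 months. For the p = 0.60 gain of 1.6 enrollees (1.585 before rounding):

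- A = 2 (13 per year): 1.585/13 × 12 = 1.5 months
- A = 3 (8.67 per year): 1.585/8.67 × 12 = 2.2 months
- A = 4 (6.5 per year): 1.585/6.5 × 12 = 2.9 months

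With accrual continuing at a constant rate, the average number of implants avoided equals the gain in enrollees: 1.6 at p = 0.60, or about 1 to 2.

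**Context: what the rule can detect.** The 4-7 band also contains scores 6 and 7, so the planning rate of RUST 5 or less is at most 33%. P(X ≥ 6 | 10, p) is 7.3% at 0.33 and 7.7% at 4/12. It is 0.23% if only half of that band scores 5 or less (assumed; the split is not given). An even chance of stopping needs a true rate of about 55%.

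**The case against.** The strongest reply is that the gain is slight and other safeguards exist. Section 6.4 sets up an independent DSMB and gives the research monitor authority to stop the protocol, so six recorded failures need not be ignored. This stands as a limit on the harm, but Section 6.4 ties neither body to this rule, and the timing sentence directs the decision to a later date. The accrual pattern is also assumed, and the visit window of ±4 weeks could blur a gain of this size.

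Two stronger readings are tempting.

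- **That the wait exposes most of the arm.** With even accrual, about 10 + 26/A children (23, 19 or 16 for A = 2, 3 or 4) have been implanted when the tenth reaches 12 months. Nearly all of that comes from having a 12-month endpoint. The wait itself accounts for about 1 to 2.
- **That the rule fails as protection against an ineffective implant,** because it would stop an arm equal to control at most about 7-8% of the time. The plan never gives it that purpose. Complete failure of union, a cut at 5 and permissive wording describe a guard against gross failure. Section 1.0 wants the better group as a future control arm regardless of results, which is a reason to finish the trial if the arms are equal. The ceiling also rests on 12 patients: the exact 95% interval for 4/12 is 10% to 65%, and at 65% the rule would stop 75% of the time.

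It might also be inferred that failure should be counted as anything short of the Section 5.3 definition, where "a RUST score of 9-12, with at least 2 evaluable cortices having a score of 3, will be considered to be healed". The documents do not support that change. With 6 of 10 kept, the stopping chance for an arm equal to control would lie anywhere from 7% to 92%, because the split of the 8-9 band is not given. In the plan's own NF1 series treated with BMP-2 (Section 3.7), 9 of 16 healed by that series' definition. That leaves 7/16 = 44% unhealed, and the boundary would be crossed about 24% of the time, which could end the whole study.

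**Conclusion.** The point holds as one of timing. The plan defers a decision that may already be settled, and the deferral has no statistical benefit. That the stopping chance is unaffected is exact and needs no assumption. The size of the gain rests on an assumed 60% failure rate, even accrual over 2 to 4 years and 12-month visits on schedule: about 1.5 to 3 months and 1 to 2 children, on average, among trials that reach the boundary. It is a small improvement in safety at no cost, and it does not affect the primary analysis. The absence of printed stopping chances is missing detail. It is not evidence that the boundary is set wrongly.

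**What to change.** In Section 6.2, Early Stopping Rule, replace the timing sentence with: *The boundary is met, and the decision is taken, when the sixth such failure among the first 10 BMP-2 enrollees is recorded, or at the tenth 12-month assessment at the latest.* Leave the failure definition, the count of 6 of 10 and the permissive wording as they are.

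Optionally, state that the rule guards against gross failure, and print its chances beside the toxicity table: 7.3% at a true rate of 0.33, 37.7% at 0.50, 63.3% at 0.60 and 85.0% at 0.70.

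The cost is wording in the plan and in any DSMB charter, plus scoring the 12-month radiographs of the first ten BMP-2 children as they arrive. Sample size and the chance of stopping do not change.
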